# 5.1.4 Deaths

As described in Section 1.3.3, in the RPCP of the Phase II clinical trials in mild-tomoderate Alzheimer's disease (ABBY and BLAZE), there were 5 deaths. All 5 deaths occurred in patients treated with crenezumab, and none were assessed as related to study drug by the investigator. This represents 1.4% (5/346) of patients receiving crenezumab compared with 0.0% (0/176) of patients receiving placebo. The causes of death are in line with published literature showing no prevalent cause of death among Alzheimer's disease treatment trials (Henley et al. 2012; Henley et al. 2014; Doody et al. 2014).

A causal relationship between crenezumab and the fatal events cannot be established or ruled out. Fatal events will continue to be monitored closely for the identification of any potential pattern (e.g., a more frequent cause of death) or a particular population group at risk (e.g., gender, age group, particular comorbidity). Exposure-adjusted rates will be assessed and compared with published background rates from a similar study population (Henley et al. 2012; Henley et al. 2014).

# 5.2 SAFETY PARAMETERS AND DEFINITIONS

Safety assessments will consist of monitoring and recording adverse events, including serious adverse events and non-serious adverse events of special interest, measurement of protocol-specified safety laboratory assessments, measurement of protocol-specified vital signs, and other protocol-specified tests that are deemed critical to the safety evaluation of the study.

Certain types of events require immediate reporting to the Sponsor, as outlined in Section 5.4.

#### 5.2.1 Adverse Events

According to the ICH guideline for Good Clinical Practice, an adverse event is any untoward medical occurrence in a clinical investigation patient administered a pharmaceutical product, regardless of causal attribution. An adverse event can therefore be any of the following:

- Any unfavorable and unintended sign (including an abnormal laboratory finding), symptom, or disease temporally associated with the use of a medicinal product, whether or not considered related to the medicinal product
- Any new disease or exacerbation of an existing disease (a worsening in the character, frequency, or severity of a known condition), except as described in Section 5.3.5.9
- Recurrence of an intermittent medical condition (e.g., headache) not present at baseline
- Any deterioration in a laboratory value or other clinical test (e.g., ECG, X-ray) that is associated with symptoms or leads to a change in study treatment or concomitant treatment or discontinuation from study drug

Crenezumab—Genentech, Inc. 58/Protocol GN28525, Version 6

• Adverse events that are related to a protocol-mandated intervention, including those that occur prior to assignment of study treatment (e.g., screening invasive procedures such as biopsies)

#### 5.2.2 Serious Adverse Events (Immediately Reportable to the Sponsor)

A serious adverse event is any adverse event that meets any of the following criteria:

- Fatal (i.e., the adverse event actually causes or leads to death)
- Life threatening (i.e., the adverse event, in the view of the investigator, places the patient at immediate risk of death)

This does not include any adverse event that had it occurred in a more severe form or was allowed to continue might have caused death.

- Requires or prolongs inpatient hospitalization (see Section 5.3.5.10)
- Results in persistent or significant disability/incapacity (i.e., the adverse event results in substantial disruption of the patient's ability to conduct normal life functions)
- Congenital anomaly/birth defect in a neonate/infant born to a mother exposed to study drug
- Significant medical event in the investigator's judgment (e.g., may jeopardize the patient or may require medical/surgical intervention to prevent one of the outcomes listed above)

The terms "severe" and "serious" are not synonymous. Severity refers to the intensity of an adverse event (rated as mild, moderate, or severe, or according to National Cancer Institute Common Terminology Criteria for Adverse Events (NCI CTCAE) criteria; see Section 5.3.3); the event itself may be of relatively minor medical significance (such as severe headache without any further findings).

Severity and seriousness need to be independently assessed for each adverse event recorded on the eCRF.

Serious adverse events are required to be reported by the investigator to the Sponsor immediately (i.e., no more than 24 hours after learning of the event; see Section 5.4.2 for reporting instructions).

#### 5.2.3 Non-Serious Adverse Events of Special Interest (Immediately Reportable to the Sponsor)

Non-serious adverse events of special interest are required to be reported by the investigator to the Sponsor immediately (i.e., no more than 24 hours after learning of the event; see Section 5.4.2 for reporting instructions). Adverse events of special interest for this study include the following:

• Cerebral vascular edema (ARIA-E)

Crenezumab—Genentech, Inc. 59/Protocol GN28525, Version 6

- Superficial siderosis of central nervous system (ARIA-H)
- Cerebral microhemorrhages (ARIA-H) or macrohemorrhages
- Occurrence of pneumonia regardless of severity/seriousness or relatedness with study drug. Diagnosis is to be verified by imaging (e.g., chest X-ray) (see Sections 3.4.3 and 5.1.3)
- Suspected transmission of an infectious agent by the investigational product, as defined below:

Any organism, virus, or infectious particle (e.g., prion protein transmitting transmissible spongiform encephalopathy), pathogenic or non-pathogenic, is considered an infectious agent. A transmission of an infectious agent may be suspected from clinical symptoms or laboratory findings that indicate an infection in a patient exposed to a medicinal product. This term applies only when a contamination of the study drug is suspected.

• Cases of potential drug-induced liver injury that include an elevated ALT or AST in combination with either an elevated bilirubin or clinical jaundice, as defined by Hy's law (see Section 5.3.5.6)

# 5.3 METHODS AND TIMING FOR CAPTURING AND ASSESSING SAFETY PARAMETERS

The investigator is responsible for ensuring that all adverse events (see Section 5.2.1 for definition) are recorded on the Adverse Event eCRF and reported to the Sponsor in accordance with instructions provided in this section and in Sections 5.4-5.6.

For each adverse event recorded on the Adverse Event eCRF, the investigator will make an assessment of seriousness (see Section 5.2.2 for seriousness criteria), severity (see Section 5.3.3), and causality (see Section 5.3.4).

#### 5.3.1 Adverse Event Reporting Period

Investigators will seek information on adverse events at each patient contact. All adverse events, whether reported by the patient or noted by study personnel, will be recorded in the patient's medical record and on the Adverse Event eCRF.

Adverse events occurring after informed consent has been obtained but prior to initiation of study drug, only serious adverse events caused by a protocol-mandated intervention should be reported (e.g., serious adverse events related to invasive procedures such as biopsies). No events during the screening period should be entered into the Adverse Event eCRF; they should be captured in the original study AE CRF (i.e., Abby or Blaze), if within the reported period for those.

Only adverse events and serious adverse events that are unresolved when the patient is randomized (on Day 1) in Study GN28525 should be carefully recorded over to the GN28525 eCRF Database.

**After initiation of study drug**, all adverse events and serious adverse events, regardless of relationship to study drug, will be reported until at least *8 weeks* after the last dose of study drug. After this period, investigators should report any deaths, serious adverse events, or other adverse events of special interest (see Section 5.6).

#### 5.3.2 Eliciting Adverse Event Information

A consistent methodology of non-directive questioning should be adopted for eliciting adverse event information at all patient evaluation time points. Examples of non-directive questions include the following:

"How have you felt since your last clinic visit?"

"Have you had any new or changed health problems since you were last here?"

#### 5.3.3 Assessment of Severity of Adverse Events

The adverse event severity grading scale for the NCI CTCAE (v4.0) will be used for assessing adverse event severity. Table 2 will be used for assessing severity for adverse events that are not specifically listed in the NCI CTCAE.

#### Table 1 Adverse Event Severity Grading Scale

Grade	Severity
1	Mild; asymptomatic or mild symptoms; clinical or diagnostic observations only; or intervention not indicated
2	Moderate; minimal, local, or non-invasive intervention indicated; or limiting age-appropriate instrumental activities of daily living a
3	Severe or medically significant, but not immediately life-threatening; hospitalization or prolongation of hospitalization indicated; disabling; or limiting self-care activities of daily living b,c
4	Life-threatening consequences or urgent intervention indicated d
5	Death related to adverse event d

NCI CTCAE = National Cancer Institute Common Terminology Criteria for Adverse Events. Note: Based on the NCI CTCAE (v4.0), which can be found at:

http://evs.nci.nih.gov/ftp1/CTCAE/CTCAE\_4.03\_2010-06-14\_QuickReference\_8.5x11.pdf

- a Instrumental activities of daily living refer to preparing meals, shopping for groceries or clothes, using the telephone, managing money, etc.
- b Examples of self-care activities of daily living include bathing, dressing and undressing, feeding one's self, using the toilet, and taking medications, as performed by patients who are not bedridden.
- c If an event is assessed as a "significant medical event," it must be reported as a serious adverse event (see Section 5.4.2 for reporting instructions), per the definition of serious adverse event in Section 5.2.2.
- d Grade 4 and 5 events must be reported as serious adverse events (see Section 5.4.2 for reporting instructions) per the definition of serious adverse event in Section 5.2.2.

# 5.3.4 Assessment of Causality of Adverse Events

Investigators should use their knowledge of the patient, the circumstances surrounding the event, and an evaluation of any potential alternative causes to determine whether or not an adverse event is considered to be related to the study drug, indicating "yes" or "no" accordingly. The following guidance should be taken into consideration (see Table 3):

- Temporal relationship of event onset to the initiation of study drug
- Course of the event, considering the effects of discontinuation of study drug, or reintroduction of study drug (where applicable)
- Known association of the event with the study drug or with similar treatments
- Known association of the event with the disease under study
- Presence of risk factors in the patient or use of concomitant medications known to increase the occurrence of the event
- Presence of non-treatment-related factors that are known to be associated with the occurrence of the event

# Table 2 Causal Attribution Guidance

Is the adverse event suspected to be caused by the study drug on the basis of facts, evidence, science-based rationales, and clinical judgment?

- YES There is a plausible temporal relationship between the onset of the adverse event and administration of the study drug, and the adverse event cannot be readily explained by the patient's clinical state, intercurrent illness, or concomitant therapies; and/or the adverse event follows a known pattern of response to the study drug; and/or the adverse event abates or resolves upon discontinuation of the study drug and, if applicable, reappears upon re-challenge.
- NO AEs will be considered related, unless they fulfill the criteria as specified below. Evidence exists that the adverse event has an etiology other than the study drug (e.g., preexisting medical condition, underlying disease, intercurrent illness, or concomitant medication); and/or the adverse event has no plausible temporal relationship to administration of the study drug (e.g., cancer diagnosed 2 days after first dose of study drug).

For patients receiving combination therapy, causality will be assessed individually for each protocol-mandated therapy.

#### 5.3.5 Procedures for Recording Adverse Events

Investigators should use correct medical terminology/concepts when recording adverse events on the Adverse Event eCRF. Avoid colloquialisms and abbreviations.

Only one adverse event term should be recorded in the event field on the Adverse Event eCRF.

# 5.3.5.1 Diagnosis versus Signs and Symptoms

Adverse events that occur during or within 24 hours after study drug infusion should be captured as individual signs and symptoms rather than a diagnosis of allergic reaction or infusion reaction.

A diagnosis (if known) should be recorded on the Adverse Event eCRF rather than individual signs and symptoms (e.g., record only liver failure or hepatitis rather than jaundice, asterixis, and elevated transaminases). However, if a constellation of signs and/or symptoms cannot be medically characterized as a single diagnosis or syndrome at the time of reporting, each individual event should be recorded on the Adverse Event eCRF. If a diagnosis is subsequently established, all previously reported adverse events based on signs and symptoms should be nullified and replaced by one adverse event report based on the single diagnosis, with a starting date that corresponds to the starting date of the first symptom of the eventual diagnosis.

Diagnoses for cerebral vasogenic edema (ARIA-E), superficial siderosis of central nervous system, cerebral microhemorrhage, and cerebral macrohemorrhage will be made based on MRI. It is suggested that the descriptions "cerebral vasogenic edema," "superficial siderosis of central nervous system," "cerebral microhemorrhage," and "cerebral hemorrhage," be used for AE and SAE reporting purposes.

# 5.3.5.2 Adverse Events Occurring Secondary to Other Events

In general, adverse events occurring secondary to other events (e.g., cascade events or clinical sequelae) should be identified by their primary cause, with the exception of severe or serious secondary events. However, medically significant adverse events occurring secondary to an initiating event that are separated in time should be recorded as independent events on the Adverse Event eCRF. For example:

- If vomiting results in mild dehydration with no additional treatment in a healthy adult, only vomiting should be reported on the eCRF.
- If vomiting results in severe dehydration, both events should be reported separately on the eCRF.
- If a severe gastrointestinal hemorrhage leads to renal failure, both events should be reported separately on the eCRF.
- If dizziness leads to a fall and consequent fracture, all three events should be reported separately on the eCRF.
- If neutropenia is accompanied by a mild, non-serious infection, only neutropenia should be reported on the eCRF.
- If neutropenia is accompanied by a severe or serious infection, both events should be reported separately on the eCRF.

All adverse events should be recorded separately on the Adverse Event eCRF if it is unclear as to whether the events are associated.

# 5.3.5.3 Persistent or Recurrent Adverse Events

A persistent adverse event is one that extends continuously, without resolution between patient evaluation time points. Such events should only be recorded once in the Adverse Event eCRF unless their severity increases. If a persistent AE becomes more severe, it should be recorded as a separate event on the Adverse Event eCRF. The initial (less severe) adverse event report should be updated to indicate that the event resolved on the date just prior to the day the event became more severe. If a persistent adverse event eCRF and reported to the Sponsor immediately (i.e., no more than 24 hours after learning that the event became serious; see Section 5.4.2 for reporting instructions). The initial (non-serious) adverse event report should be updated to indicate that the event that the event resolved on the date just prior to the day the event should be updated to indicate that the event has a separate event performed as a separate event on the Adverse Event eCRF and reported to the Sponsor immediately (i.e., no more than 24 hours after learning that the event became serious; see Section 5.4.2 for reporting instructions). The initial (non-serious) adverse event report should be updated to indicate that the event resolved on the date just prior to the day the event became serious.

A recurrent adverse event is one that occurs and resolves between patient evaluation time points and subsequently recurs. All recurrent adverse events should be recorded on the Adverse Event eCRF.

# 5.3.5.4 Abnormal Laboratory Values

Not every laboratory abnormality qualifies as an adverse event. A laboratory test result should be reported as an adverse event if it meets any of the following criteria:

- Accompanied by clinical symptoms
- Results in a change in study treatment (e.g., dosage modification, treatment interruption, or treatment discontinuation)
- Results in a medical intervention (e.g., potassium supplementation for hypokalemia) or a change in concomitant therapy
- Clinically significant in the investigator's judgment

For oncology trials, certain abnormal values may not qualify as adverse events.

It is the investigator's responsibility to review all laboratory findings. Medical and scientific judgment should be exercised in deciding whether an isolated laboratory abnormality should be classified as an adverse event.

If a clinically significant laboratory abnormality is a sign of a disease or syndrome (e.g., alkaline phosphatase and bilirubin 5 times the upper limit of normal [ULN] associated with cholestasis), only the diagnosis (i.e., cholestasis) should be recorded on the Adverse Event eCRF.

If a clinically significant laboratory abnormality is not a sign of a disease or syndrome, the abnormality itself should be recorded on the Adverse Event eCRF, along with a descriptor indicating if the test result is above or below the normal range (e.g., "elevated potassium," as opposed to "abnormal potassium"). If the laboratory abnormality can be characterized by a precise clinical term per standard definitions, the clinical term should

be recorded as the adverse event. For example, an elevated serum potassium level of 7.0 mEq/L should be recorded as "hyperkalemia."

Observations of the same clinically significant laboratory abnormality from visit to visit should not be repeatedly recorded on the Adverse Event eCRF, unless the etiology changes. The initial severity of the event should be recorded, and the severity or seriousness should be updated any time the event worsens.

# 5.3.5.5 Abnormal Vital Sign Values

Not every vital sign abnormality qualifies as an adverse event. A vital sign result should be reported as an adverse event if it meets any of the following criteria:

- Accompanied by clinical symptoms
- Results in a change in study treatment (e.g., dosage modification, treatment interruption, or treatment discontinuation)
- Results in a medical intervention or a change in concomitant therapy
- Clinically significant in the investigator's judgment

It is the investigator's responsibility to review all vital sign findings. Medical and scientific judgment should be exercised in deciding whether an isolated vital sign abnormality should be classified as an adverse event.

If a clinically significant vital sign abnormality is a sign of a disease or syndrome (e.g., high blood pressure), only the diagnosis (i.e., hypertension) should be recorded on the Adverse Event eCRF.

Observations of the same clinically significant vital sign abnormality from visit to visit should not be repeatedly recorded on the Adverse Event eCRF, unless the etiology changes. The initial severity of the event should be recorded, and the severity or seriousness should be updated any time the event worsens.

# 5.3.5.6 Abnormal Liver Function Tests

The finding of an elevated ALT or AST (> $3 \times ULN$ ) in combination with either an elevated total bilirubin (> $2 \times ULN$ ) or clinical jaundice in the absence of cholestasis or other causes of hyperbilirubinemia is considered to be an indicator of severe liver injury. Therefore, investigators must report as an adverse event the occurrence of either of the following:

- Treatment-emergent ALT or AST  $> 3 \times ULN$  in combination with total bilirubin  $> 2 \times ULN$
- Treatment-emergent ALT or AST > 3 × ULN in combination with clinical jaundice

The most appropriate diagnosis or (if a diagnosis cannot be established) the abnormal laboratory values should be recorded on the Adverse Event eCRF (see Section 5.3.5.1) and reported to the Sponsor immediately (i.e., no more than 24 hours after learning of

the event) either as a serious adverse event or a non-serious adverse event of special interest (see Section 5.4.2).

# 5.3.5.7 Deaths

All deaths that occur during the protocol-specified adverse event reporting period (see Section 5.3.1), regardless of relationship to study drug, must be recorded on the Adverse Event eCRF and immediately reported to the Sponsor (see Section 5.4.2). This includes death attributed to progression of Alzheimer's disease.

Death should be considered an outcome and not a distinct event. The event or condition that caused or contributed to the fatal outcome should be recorded as the single medical concept on the Adverse Event eCRF. Generally, only one such event should be reported. The term "sudden death" should only be used for the occurrence of an abrupt and unexpected death due to presumed cardiac causes in a patient with or without preexisting heart disease, within 1 hour of the onset of acute symptoms or, in the case of an unwitnessed death, within 24 hours after the patient was last seen alive and stable. If the cause of death is unknown and cannot be ascertained at the time of reporting, "unexplained death" should be recorded on the Adverse Event eCRF. If the cause of death later becomes available (e.g., after autopsy), "unexplained death" should be replaced by the established cause of death.

If the death is attributed to progression of Alzheimer's disease, "Alzheimer's disease progression" should be recorded on the Adverse Event eCRF.

# 5.3.5.8 Pre-Existing Medical Conditions

A pre-existing medical condition is one that is present at the screening visit for this study. Such conditions should be recorded on the General Medical History and Baseline Conditions eCRF.

A preexisting medical condition should be recorded as an adverse event only if the frequency, severity, or character of the condition worsens during the study. When recording such events on the Adverse Event eCRF, it is important to convey the concept that the preexisting condition has changed by including applicable descriptors (e.g., "more frequent headaches").

# 5.3.5.9 Worsening of Alzheimer's Disease

Medical occurrences or symptoms of deterioration that are anticipated as part of Alzheimer's disease should be recorded as an adverse event if judged by the investigator to have unexpectedly worsened in severity or frequency or changed in nature at any time during the study. When recording an unanticipated worsening of Alzheimer's disease on the Adverse Event eCRF, it is important to convey the concept that the condition has changed by including applicable descriptors (e.g., "accelerated Alzheimer's disease")

# 5.3.5.10 Hospitalization or Prolonged Hospitalization

Any adverse event that results in hospitalization (i.e., in-patient admission to a hospital) or prolonged hospitalization should be documented and reported as a serious adverse event (per the definition of serious adverse event in Section 5.2.2), except as outlined below.

The following hospitalization scenarios are not considered to be adverse events:

- Hospitalization for respite care
- Planned hospitalization required by the protocol
- Hospitalization for a preexisting condition, provided that all of the following criteria are met:
  - The hospitalization was planned prior to the study or was scheduled during the study when elective surgery became necessary because of the expected normal progression of the disease
  - The patient has not suffered an adverse event
- Hospitalization due solely to progression of Alzheimer's disease

The following hospitalization scenarios are not considered to be serious adverse events, but should be reported as adverse events instead:

• Hospitalization for an adverse event that would ordinarily have been treated in an outpatient setting had an outpatient clinic been available

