## 1.3.3.3 Serious and Non-Serious Adverse Events

During the RPCP of the Phase II program, serious adverse events were reported in 57 (16.5%) patients receiving SC or IV crenezumab, and in 21 (11.9%) patients receiving SC or IV placebo. An imbalance in serious adverse events of total lower respiratory tract infections (TLRTI; including preferred terms [PT] of pneumonia, lower respiratory tract infection [LRTI] and bronchitis) driven by pneumonia was observed in the RPCP of the Phase II program, with 6 cases versus 2 cases (1.7% vs. 1.1%) of TLRTI and 6 cases versus 1 case (1.7% vs. 0.6%) of pneumonia observed in the crenezumab and placebo arms, respectively. An imbalance in non-serious adverse

Crenezumab—Genentech, Inc. 31/Protocol GN28525, Version 6

events of TLRTI also driven by pneumonia was observed in the RPCP of the Phase II program, with 18 cases versus 6 cases (5.2% vs. 3.4%) of non-serious TLRTI, and 5 cases versus 0 cases (1.4% vs. 0%) of non-serious pneumonia observed in the crenezumab and placebo arms, respectively.

Adverse events (serious and non-serious) reported in > 5% of crenezumab or placebo patients in the RPCP of the Phase II program included urinary tract infection (11.6% vs. 11.4%, crenezumab vs. placebo, respectively), nasopharyngitis (11.3% vs. 11.9%), cerebral microhemorrhage (10.1% vs. 11.4%), fall (10.1% vs. 6.8%), upper respiratory tract infection (9.8% vs. 9.1%), headache (9.8% vs. 7.4%), anxiety (9.2% vs. 7.4%), diarrhea (8.1% vs. 9.1%), dizziness (7.5% vs. 10.2%), agitation (7.5% vs. 2.8%), arthralgia (7.2% vs. 5.1%), back pain (6.9% vs. 9.7%), nausea (6.9% vs. 6.8%), cough (5.5% vs. 2.8%), and vomiting (5.2% vs. 5.1%).

Adverse events were not related to dose in the RPCP of the Phase II Studies ABE4869g and ABE4955g.

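### The Section 5.3.5.10 exemption for hospitalization due to Alzheimer's progression is not limited to anticipated progression, so it conflicts with Sections 5.3.5.9 and 5.2.2 on how an admission for unexpected worsening is classified

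*Combined protocol and SAP*

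**What the plan says.** Four sections of the protocol bear on this.

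- **Section 5.3.5.9 (worsening of Alzheimer's disease).** Deterioration of a kind anticipated in the disease "should be recorded as an adverse event if judged by the investigator to have unexpectedly worsened in severity or frequency or changed in nature". The section offers accelerated Alzheimer's disease as a suitable descriptor. Deterioration that follows the anticipated course is not an adverse event.
- **Section 5.2.2 (serious adverse events).** One criterion of seriousness for an adverse event is "Requires or prolongs inpatient hospitalization (see Section 5.3.5.10"), so the reader is sent to 5.3.5.10 for the limits of that criterion.
- **Section 5.3.5.10 (hospitalization).** Its opening sentence makes an adverse event that leads to admission serious, subject to the exceptions that follow. The first list of exceptions names scenarios that are not adverse events at all, and it includes "Hospitalization due solely to progression of Alzheimer's disease". The bullet just above it, on pre-existing conditions, applies only if several conditions are met, one of them being "The patient has not suffered an adverse event".
- **Section 5.3.5.7 (deaths).** All deaths in the reporting period are recorded on the Adverse Event form and reported at once. "This includes death attributed to progression of Alzheimer's disease".

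**The concern.** Consider a patient whose dementia accelerates unexpectedly and who is admitted for that reason alone. Section 5.3.5.9 calls this an adverse event, and 5.2.2 would make it serious. Section 5.3.5.10 lists the admission among things that are not adverse events. Each of two sites could cite the protocol for a different classification.

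The serious classification decides how fast, and whether, the sponsor looks at the case. Section 5.4 requires reporting within 24 hours for serious adverse events, non-serious adverse events of special interest, and pregnancies. Worsening of Alzheimer's disease is not on the special-interest list in Section 5.2.3. The sponsor's prompt evaluation against cumulative experience in Section 5.7 covers serious and special-interest events. An admission that loses its serious classification loses both.

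Long-term safety is the primary objective and the study has no concurrent comparator. Uneven classification across sites would therefore pass straight into the reported rate of serious events, with no control arm to reveal it.

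**Working it through.** **Step 1. Set the rules side by side.**

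| Clinical course | Section | Classification |
|---|---|---|
| Anticipated progression, admitted | 5.3.5.9 and 5.3.5.10 | Not an adverse event; the sections agree |
| Unexpected worsening, not admitted | 5.3.5.9 | Adverse event |
| Unexpected worsening as the sole cause of admission | 5.3.5.9 with 5.2.2 | Serious adverse event, reported within 24 hours |
| Same course | 5.3.5.10 read literally | Admission is not an adverse event |
| Death attributed to progression | 5.3.5.7 | Recorded and reported at once |

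The conflict is confined to the third and fourth rows. The last row adds an inconsistency: unexpected worsening is captured without admission and progression is captured when fatal, but the step between is exempt on a literal reading.

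**Step 2. Does the cross-reference settle it?** No. Section 5.2.2 defers to 5.3.5.10, and the general rule in 5.3.5.10 yields to its own exceptions. Followed in order, the references end at the exemption.

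**Step 3. Does the wording of the exemption settle it?** It does not mention expected or anticipated progression. The pre-existing-condition bullet has both kinds of limit: one of its conditions refers to the expected course of the disease, and another is "The patient has not suffered an adverse event". Neither is attached to the Alzheimer's bullet. Section 5.3.5.10 also has a second list, for admissions that are adverse events but not serious. The Alzheimer's bullet is in the first list, not that one.

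**Step 4. Scale.** The plan gives no figure for such admissions, so there is nothing to reproduce. Section 1.3.3.5 gives serious adverse events in this extension study as of 27 May 2014: 15 subcutaneous patients (10.1%) and 18 intravenous patients (8.5%).

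- Subcutaneous denominator: 15/148 = 10.14% and 15/149 = 10.07%. Both round to 10.1%, so n is 148 or 149.
- Intravenous denominator: 18/211 = 8.53% and 18/213 = 8.45%. Both round to 8.5%, so n is 211 to 213.
- Total: 15 + 18 = 33 patients among 359 to 362, taken as about 360. Rate: 33/360 = 9.2%.
- Effect of one more patient classed as having a serious event: 100/360 = 0.28 percentage points.

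The next table assumes a number m of affected patients, each with no other serious event, at a denominator of 360.

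| m (assumed) | (33 + m)/360 |
|---|---|
| 0 | 9.2% |
| 1 | 9.4% |
| 3 | 10.0% |
| 5 | 10.6% |
| 10 | 11.9% |

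No value of m is supported by the documents. A patient who already has another serious event would not move this rate at all.

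**The case against.** The strongest reply is that the sections can be read as a whole. Section 5.2.1 sends worsening of Alzheimer's disease to 5.3.5.9, and that section separates the anticipated course from unexpected worsening. On that reading, progression in 5.3.5.10 means the anticipated course, accelerated disease is an adverse event, and the opening sentence of 5.3.5.10 makes an admission for it serious. This is plausible and may be what the sponsor intends. The text does not require it, though, and the limits on the neighbouring bullet make the silence here harder to read as implied.

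Three further points on that side stand.

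- Section 5.3.5.9 applies at any time in the study and has no exception for admitted patients, so the worsening itself should still be recorded.
- Other routes to seriousness remain in 5.2.2, including life-threatening events, lasting disability and significant medical events in the investigator's judgment. None of these points to 5.3.5.10.
- Exempting anticipated progression is a legitimate design choice and is not in dispute.

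A reader might infer that genuine serious events drop out of the primary safety outcome. The documents do not support that. Section 3.4.1 lists the frequency, nature and severity of adverse events and has no separate item for serious events. The worsening is lost altogether only where a site takes 5.3.5.10 to override 5.3.5.9.

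A reader might also tie the gap to ARIA-E or to the feeder-study imbalance in agitation. ARIA-E is an adverse event of special interest, reportable within 24 hours in its own right, and an admission caused by it is not due solely to progression. The agitation figures count adverse events that were reported, not admissions, and show nothing about this rule.

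**Conclusion.** The contradiction is in the text and is narrow. It concerns admissions caused only by worsening that meets 5.3.5.9. For these, a literal reading of 5.3.5.10 removes the serious classification, 24-hour reporting under 5.4 and expedited evaluation under 5.7, and it leaves sites free to classify like cases differently. There is no conflict for anticipated progression.

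The size is unknown. The documents do not count admissions attributed to progression, nor say how many followed unexpected worsening, and the number affected may be zero. The figure of about 0.28 percentage points per patient is a unit of scale, not an estimate of bias. It rests on denominators recovered from rounded percentages at one data cut, and on the affected patient having no other serious event.

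The point is worth correcting because the rule governs safety reporting in a study whose primary purpose is safety, and because the correction is small.

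**What to change.** Reword the bullet in Section 5.3.5.10 to read: *Hospitalization due solely to expected progression of Alzheimer's disease that does not meet Section 5.3.5.9.* Add a sentence stating that an admission for worsening that meets Section 5.3.5.9 is reported as a serious adverse event under Section 5.2.2.

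The cost is a wording change in an amendment and a note to sites. The reported rate of serious adverse events may rise slightly.
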